3.1.7 Prior and concomitant medication

Medications taken by any subject at any time during the study will be coded using the anatomical therapeutic chemical (ATC) classification system within the world health organisation (WHO) drug dictionary.

Medications will be categorised for analysis according to their onset and end dates as follows:

- Prior medications:
 - end date \leq date of first dose of IP
- Concomitant medications during on-treatment period:
 - end date $>$ date of first dose of IP and start date \leq minimum (date of last dose of IP + 35 days, date of death, date of study withdrawal), or
 - end date ongoing and start date \leq minimum (date of last dose of IP + 35 days, date of death, date of study withdrawal)
- Concomitant medications during post-treatment period (for subjects still being followed up then):
 - start date $>$ date of last dose of IP + 35 days

Essentially the above says that:

- Prior and concomitant medications are mutually exclusive.
- Concomitant medications on-treatment and post-treatment are also mutually exclusive (here, the word “concomitant” means concomitant with study procedures, irrespective of whether IP was still being taken). Specifically, a concomitant medication which started on-treatment and ended post-treatment will only be considered on-treatment.

If the medication record has a completely missing start date, the subject will be assumed to have been on the medication on the date of the first study procedure. If the medication record has a partially missing onset date (month/year or year only) which is the same as that for the end of IP treatment, it will be assumed to have started on-treatment. If the medication record has a partially missing onset date (month/year or year only) which is the same as that for the start of IP treatment, it will be assumed to have started before treatment.

If the medication record has a completely missing end date, the subject will be assumed to have been on the medication on the date of study completion or withdrawal. If the medication record has a partially missing end date (month/year or year only) which is the same as that for start of IP treatment, it will be assumed to have ended on-treatment. If the medication record has a partially missing end date (month/year or year only) which is the same as that for end of IP treatment, it will be assumed to have ended post-treatment.

3.1.8 Definition of subgroups

The following subgroups are defined for the purposes of efficacy subgroup analysis (indicated with a *) and/or demographic and baseline summaries:

- * Stratification factor - screening blood eosinophils strata (Visit 1): < 150 cells/ μ L, 150 - < 300 cells/ μ L, \geq 300 cells/ μ L
- * Baseline blood eosinophils group based on values at randomisation visit (Visit 3b): < 150 cells/ μ L, 150 - < 300 cells/ μ L, \geq 300 cells/ μ L
- * Gender: Male, Female
- * Race: White, Black or African American, Asian, Other
- * Age category: adults (\geq 65 years), adults (18 - <65 years)
- * Baseline FeNO group: <25 ppb, \geq 25 ppb
- Baseline (any) specific IgE status (FEIA): Any FEIA positive, All FEIA negative, Unknown FEIA
 - “Any FEIA positive” requires 1 or more specific IgE panels using fluorescent enzyme immunoassay (FEIA) to be positive. Provided that at least one IgE panel is positive, no further requirement is made for data on all 12 panels to be available.
 - “All FEIA negative” requires all 12 specific IgE panels to be negative. If there are fewer than 12 panels with data available and none of these is positive, then IgE status is considered “Unknown FEIA”.
 - Positive is defined as a value \geq 0.35 kU/L
- * Baseline perennial specific IgE status (FEIA): Any perennial FEIA positive, All perennial FEIA negative, Unknown perennial FEIA
 - “Any perennial FEIA positive” requires 1 or more specific IgE (FEIA) panels to be positive. Provided that at least one IgE panel is positive, no further requirement is made for data on all 8 panels to be available.
 - “All perennial FEIA negative” requires all 8 specific IgE panels to be negative. If there are fewer than 8 panels with data available and none of these is positive, then IgE status is considered “Unknown perennial FEIA”.
 - Positive is defined as a value \geq 0.35 kU/L. The 8 panels include: American Cockroach, Cat Dander, D. farina, D. pteronyssinus, Dog Dander, German Cockroach, Mould Mix, Oriental Cockroach.
- Baseline seasonal specific IgE status (FEIA): Any seasonal FEIA positive, All seasonal FEIA negative, Unknown seasonal FEIA

- “Any seasonal FEIA positive” requires 1 or more specific IgE (FEIA) panels to be positive. Provided that at least one IgE panel is positive, no further requirement is made for data on all 4 panels to be available.
- “All seasonal FEIA negative” requires all 4 specific IgE panels to be negative. If there are fewer than 4 panels with data available and none of these is positive, then IgE status is considered “Unknown seasonal FEIA”
- Positive is defined as a value ≥ 0.35 kU/L. The 4 panels include: Grass Mix Pollen, Silver Birch Pollen, Weed Mix Pollen, Japanese Cedar.
- * Baseline total serum IgE group: $<$ median, \geq median
- * Baseline interleukin-5 (IL-5) group: $<$ median, \geq median
- * Baseline IL-13 group: $<$ median, \geq median
- ICS dose at study entry: medium, high (as defined in CSP Appendix F)
- OCS at baseline: present, absent
 - OCS at baseline will be defined as OCS administered at baseline for disease under study
- Baseline body mass index (BMI): <18.5 kg/m², 18.5 - <25.0 kg/m², 25.0 - <30.0 kg/m², ≥ 30.0 kg/m² Geographical region: North America [incl. Canada and USA], Western Europe [incl. Denmark, Germany, and UK]
- Reversibility in FEV1 %: $<12\%$, $\geq 12\%$
 - Reversibility in FEV1 (%) is $[\text{post-bronchodilator FEV1 (L)} - \text{pre-bronchodilator FEV1 (L)}] / \text{pre-bronchodilator FEV1 (L)} * 100\%$
- Asthma controller therapy: 1, >1
- Country

3.1.9 Disposition

The following definitions will be used for time to event variables in Kaplan-Meier disposition plots:

Time to last dose of IP

Time to last dose of IP will be defined as follows:

$$\text{Time to last dose (days)} = [\text{Date of last dose of IP from eCRF} - \text{date of first dose of IP}] + 1.$$

Date of last dose of IP will be the date of last dose taken from the “Discontinuation of Investigational Product” eCRF page for all subjects; those who prematurely discontinue IP as well as those who complete IP dosing as per protocol.

Time to premature study withdrawal

Time to premature study withdrawal will be defined as follows:

Time to premature study withdrawal (days) = [study withdrawal date from eCRF – date of randomisation] + 1.

Study withdrawal date will be the completion or discontinuation date from the “Disposition” eCRF page, where any subject status other than “Completed” has been entered.

Subjects who did not prematurely withdraw from study will be censored at the completion or discontinuation date from the “Disposition” eCRF page, where subject status of “Completed” has been entered.

3.2 Derivation of efficacy variables

3.2.1 Primary endpoints

3.2.1.1 Change from baseline to EOT in number of airway inflammatory cells per mm²

Bronchial biopsies will be performed at baseline (Visit 3b) and EOT . The number of airway inflammatory cells per mm² will be determined by microscopic evaluation of bronchoscopic biopsies separately for eosinophils, neutrophils, T cells (CD3+, and CD4+), mast cells tryptase+, and mast cells chymase+.

The primary efficacy variables will be the change, expressed as a ratio, in number of airway inflammatory cells per mm² from baseline to EOT i.e. (EOT/baseline) for eosinophils, neutrophils, T cells (CD3+, and CD4+), mast cells tryptase+, and mast cells chymase+.. Each cell type will be analysed separately.

Absolute change from baseline to EOT in number of airway inflammatory cells per mm² for eosinophils, neutrophils, T cells (CD3+, and CD4+), mast cells tryptase+, and mast cells chymase+ are considered as supportive variables to the corresponding primary variables.

3.2.2 Secondary endpoints

3.2.2.1 Change from baseline to EOT in RBM thickness

RBM thickness (µm) will be determined by microscopic evaluation of bronchoscopic biopsies at baseline (Visit 3b) and EOT .

The change, expressed as ratio, in RBM thickness from baseline to EOT i.e. (EOT/baseline), will be a secondary outcome variable.

Absolute change from baseline to EOT in RBM thickness is considered as a supportive variable.

3.2.2.2 Change from baseline to EOT in % airway epithelial integrity

The % airway epithelial integrity, including intact, damaged, and denuded epithelium %, will be determined by microscopic evaluation of bronchoscopic biopsies at baseline (Visit 3b) and EOT.

The change, expressed as a ratio, in % airway epithelial integrity from baseline to EOT i.e. (EOT/baseline), will be a secondary outcome variable.

3.2.2.3 Change from baseline to EOT in number of airway inflammatory cells per mm² across the spectrum of T2 status

Transcriptomic analysis will be performed on the RNA sample obtained from bronchial brushing at baseline (Visit 3b) and EOT (Visit 11). The three gene mean, derived from epithelial expression levels of periostin (POSTN), chloride channel accessory 1 (CLCA1), and serpin family B member 2 (SERPINB2), has been demonstrated as a surrogate marker of T2-driven inflammation in mild to moderate asthmatics. This epithelial gene expression signature will be used to retrospectively determine the degree of T2 status of each individual at randomisation (Visit 3b).

The change, expressed as a ratio, in number of airway inflammatory cells per mm² from baseline to EOT i.e. (EOT/baseline) across the spectrum of T2 status for eosinophils, neutrophils, T cells (CD3+, and CD4+), mast cells tryptase+, and mast cells chymase+ were the secondary outcome variables. Each cell type would have been analysed separately.

Absolute change from baseline to EOT in number of airway inflammatory cells per mm² across the spectrum of T2 status for eosinophils, neutrophils, T cells (CD3+, and CD4+), mast cells tryptase+, and mast cells chymase+ are considered as supportive variables.

3.2.3 Exploratory endpoints

CCI

[Redacted content]

- CCI [redacted]

- [redacted]

- [redacted]

- [redacted]

- [redacted]

- [redacted]

- [redacted]

- [redacted]

- [redacted]

- [redacted]

- [redacted]

- [redacted]

- [redacted]

[redacted]

[redacted]

[redacted]

[redacted]

[redacted]

- [redacted]

- [redacted]

○ CCI

[Redacted]

■ [Redacted]

■ [Redacted]

■ [Redacted]

■ [Redacted]

■ [Redacted]

[Redacted]

■ [Redacted]

■ [Redacted]

■ [Redacted]

■ [Redacted]

[Redacted]

[Redacted]

The change, expressed as a ratio, from baseline to EOT i.e. (EOT/baseline), will also be

CCI [REDACTED]

[REDACTED]

[REDACTED]

[REDACTED]

[REDACTED]

[REDACTED]

[REDACTED]

[REDACTED]

[REDACTED]

[REDACTED]

[REDACTED]

[REDACTED]

[REDACTED]

[REDACTED]

[REDACTED]

[REDACTED]

[REDACTED]

[REDACTED]

[REDACTED]

[REDACTED]

- CCI [redacted]

[redacted]

[redacted]

[redacted]

[redacted]

[redacted]

[redacted]

[redacted]

[redacted]

[redacted]

[redacted]

[redacted]

[redacted]

[redacted]

[redacted] :

CCI

[Redacted]

[Redacted]

[Redacted]

[Redacted]

[Redacted]

[Redacted]

[Redacted]

[Redacted]

[Redacted]

[Redacted]

[Redacted]

[Redacted]

[Redacted]

[Redacted]

[Redacted]

[Redacted]

[Redacted]

[Redacted]

- CCI

3.3 Derivation of Safety variables

3.3.1 Exposure to IP and treatment compliance

Extent of exposure to IP is defined as the number of days between the date of first dose of IP and the date of last dose of IP inclusive plus the number of days allowance for the dosing interval specified in on-treatment period for safety variables in Section 3.1.5, i.e.:

Extent of exposure (days) = minimum (date of last dose of IP + 35 days; date of death; date of study withdrawal) – date of first dose of IP + 1

This calculation does not consider any gaps in exposure caused by the subject missing one or more intermediate scheduled 4-weekly doses. Such cases will be identified in the CSR if they occur, but will not explicitly be accounted for in any analysis.

The total subject-years exposure for a treatment group will be derived as the sum of the individual subject extents of exposure (days) for that treatment group and divided by 365.25.

Treatment compliance will be calculated as follows:

Treatment compliance (%) = (total number of actual dosing occasions/total number of expected dosing occasions) x 100%

In order to allow for subjects who discontinue IP early in the compliance calculation, the number of expected dosing occasions will be calculated as the number of scheduled dosing visits up to and including the last available dosing visit for that subject.

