1.2 Study design

[figure not shown]
This is a phase 2, multicentre, randomised, double-blind, placebo-controlled, parallel group study to evaluate the effect of tezepelumab on airway inflammation in approximately 110 adults with inadequately controlled moderate-to-severe asthma. Subjects will have background asthma therapy of medium- or high dose inhaled corticosteroids (ICS) plus at least one additional asthma controller medication, such as a long-acting β 2-agonist (LABA), leukotriene receptor antagonist (LTRA), long-acting muscarinic antagonist (LAMA), cromone, and theophylline, with or without maintenance oral corticosteroids (OCS) from screening and throughout the study including the follow-up period.

The study will consist of a screening/run-in period of up to 4 weeks, a treatment period of 28 weeks and a post-treatment follow-up period of 12 weeks. One dose level of tezepelumab, 210 mg will be compared with placebo administered subcutaneously every 4 weeks (Q4W) over the treatment period. Subjects who discontinue investigational product (IP) during the study will be encouraged to undergo appropriate study visits/procedures for the full 40-week period. Any new treatments that are initiated will be recorded. Subjects who complete the 28-week study visit will complete a 12 week off-treatment follow-up period for assessment of safety parameters and ADAs. During the COVID-19 pandemic, there is an option for patients to have an extra dose every 4 weeks up to 6 additional doses, as needed. For the last follow up visit, a phone call and/or a virtual visit can replace an on-site visit.

The study aims to randomise subjects across the spectrum of T2 status. To ensure this, the study will randomise approximately 30% of subjects with < 150 blood eosinophils/ μL , approximately 30% of subjects with $150 - < 300$ blood eosinophils/ μL and approximately 40% of subjects with ≥ 300 blood eosinophils/ μL .

For an overview of the study design see Figure 1.

Figure 1 Study Design

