The number of subjects with missed IP doses due to COVID-19, including consecutive missed doses, will be summarised by treatment group. In addition, the number of IP doses administered by location (home, other) will be summarised by treatment group, for the safety analysis set.

Section 4.2.4.1 Primary outcome variables - primary analysis

To investigate any difference in treatment effect due to any additional IP doses administered to subjects at unscheduled weeks 28, 32, 36, 40, 44 and 48 during the COVID-19 pandemic outbreak, additional sensitivity analysis will be performed including only subjects in the evaluable analysis set who had an EOT assessment at Week 28. Analyses of the primary endpoints of within subject change, expressed as a ratio, from baseline to Week 28 in airway submucosal inflammatory cells will be performed separately for eosinophils, neutrophils, T cells (CD3+, and CD4+), mast cells tryptase+ and mast cells chymase+, using the same ANCOVA model described for the primary variables in Section 4.2.1. Results will also be included in the forest plot for the primary. Descriptive statistics will also be presented.

Section 4.2.8.1 Adverse Events

The number and percentage of subjects reporting COVID-19 AEs (as defined based on the COVID-19 MedDRA terms) will be summarised by system organ class (SOC) and preferred term (PT) for the on-treatment and on-study periods.

In addition, if there are more than 10 subjects reporting COVID-19 AEs, then the AE listing will be repeated including only these subjects, with details of all AEs reported by these subjects

A listing of subjects tested for COVID-19 and including test result will be provided.

SIGNATURE PAGE

This is a representation of an electronic record that was signed electronically and this page is the manifestation of the electronic signature

Document Name: d5180c00013-sap-ed-3		
Document Title:	Statistical Analysis Plan Edition 3 15Nov2020	
Document ID:	Doc ID-003970585	
Version Label:	3.0 CURRENT LATEST APPROVED	
Server Date (dd-MMM-yyyy HH:mm 'UTC'Z)	Signed by	Meaning of Signature
18-Nov-2020 20:45 UTC	PPD [REDACTED]	Content Approval
18-Nov-2020 20:36 UTC	PPD [REDACTED]	Author Approval

Notes: (1) Document details as stored in ANGEL, an AstraZeneca document management system.

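### As written, SAP 3.3.1 counts COVID-19 additional doses in the compliance numerator but not the denominator, so the percentage can exceed 100% and offset missed regular doses

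*SAP*

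**What the plan says.** SAP Section 3.3.1 gives the formula "Treatment compliance (%) = (total number of actual dosing occasions/total number of expected dosing occasions) x 100", expressed as a percentage. The numerator carries no exclusion. The expected number of occasions "will be calculated as the number of scheduled dosing visits up to and including the last available dosing visit" for that subject; the stated purpose of that cut-off is to allow for subjects who stop investigational product early.

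Section 1.2 sets out "a treatment period of 28 weeks" with product "administered subcutaneously every 4 weeks (Q4W) over the treatment period". It then adds that during the pandemic "there is an option for patients to have an extra dose every 4 weeks up to 6 additional doses, as needed". Appendix 8.3 refers to "any additional IP doses administered to subjects at unscheduled weeks 28, 32, 36, 40, 44 and 48". The footnote to Table 1 in Section 3.1.6 also calls the pandemic visits unscheduled. It lets them run to week 48 and places the EOT assessments four weeks after the last dose.

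Section 4.2.3 summarises compliance by treatment group in the safety analysis set. Neither Section 3.3.1, Section 4.2.3 nor Appendix 8.3 says how additional doses count in compliance.

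**The concern.** The two parts of the ratio count different things. An additional dose is an actual dosing occasion, so it enters the numerator. Its visit is described as unscheduled, so on the plain wording it is not among the scheduled dosing visits in the denominator. This has two consequences:

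- A subject with any additional dose and no missed dose exceeds 100%.
- A subject who missed regular doses and later received additional ones has the misses cancelled in the percentage.

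The November 2020 edition adapted the evaluable set, the study periods and the visit windows to additional dosing. No visible row of the amendment history mentions Section 3.3.1, although some rows are redacted. An oversight is the likely explanation.

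At stake is the by-arm compliance summary. The other by-arm summaries do not fully replace it. Total dosing occasions mix regular and additional doses in the same way. The extent of exposure ignores gaps. The summary of missed doses in Appendix 8.3 covers only those attributed to COVID-19.

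**Working it through.** The plan states no compliance figure to reproduce, so this is a direct count.

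**Inputs**

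- Regular doses: Section 1.2 gives 4-weekly dosing over a 28-week treatment period. Table 1's footnote puts EOT four weeks after the last dose, and Appendix 8.3 lists week 28 as an additional-dose week. Regular doses therefore fall at weeks 0, 4, 8, 12, 16, 20 and 24, which is seven. This number is derived, not stated.
- Additional doses: up to six (Section 1.2), matching the six weeks listed in Appendix 8.3. The footnote to Table 1 implies fewer: with EOT at week 48 at the latest and four weeks after the last dose, the last dose is at week 44. That leaves weeks 28, 32, 36, 40 and 44, which is five.

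**Formulas**, with m regular doses missed and k additional doses received, for a subject whose last dosing visit is at or after week 24:

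- As written: (7 − m + k) / 7
- Extras in both terms: (7 − m + k) / (7 + k)
- Extras in neither term (regular doses only): (7 − m) / 7

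**No missed doses (m = 0), as written**

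| k | Calculation | Compliance |
|---|---|---|
| 1 | 8/7 | 114.3% |
| 2 | 9/7 | 128.6% |
| 3 | 10/7 | 142.9% |
| 4 | 11/7 | 157.1% |
| 5 | 12/7 | 171.4% |
| 6 | 13/7 | 185.7% |

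Both matched definitions give 100% in every row.

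**Missed regular doses followed by additional doses**

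| m | k | As written | Both terms | Neither term |
|---|---|---|---|---|
| 2 | 2 | 7/7 = 100% | 7/9 = 77.8% | 5/7 = 71.4% |
| 3 | 3 | 7/7 = 100% | 7/10 = 70.0% | 4/7 = 57.1% |
| 2 | 6 | 11/7 = 157.1% | 11/13 = 84.6% | 5/7 = 71.4% |

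The last row shows that counting extras in both terms brings the figure below 100% but still dilutes missed regular doses.

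**Arm-level illustration, with assumed counts.** Take 55 subjects, of whom 15 are fully dosed with three extras. The other 40 have no extras and each missed one regular dose before their last dosing visit at week 24.

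- As written: (15 × 142.9% + 40 × 85.7%) / 55 = 101%.
- Matched, by either definition: (15 × 100% + 40 × 85.7%) / 55 = 90%.

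The SAP does not say how many subjects had additional doses, so the actual arm-level shift is unknown.

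**The case against.** Four objections deserve an answer.

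*The denominator is specific to the subject.* It runs to that subject's own last dosing visit, and additional doses keep the 4-weekly interval, so a programmer might treat those visits as expected. This does not rescue the text. The cut-off only says where counting stops; what is counted is still scheduled dosing visits. It does stand that the SAP never defines that term and that the protocol's schedule is not at hand. If two programmers can read the rule differently, it needs a sentence in any case.

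*A reader might infer that the plan hides missed doses.* The document does not support that. Section 4.2.3 lists every administration and every missed dose. Section 3.3.1 says gaps will be identified in the CSR. Appendix 8.3 summarises COVID-19 misses by arm, including consecutive ones, and lists affected subjects. Only the percentage can mask a miss.

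*A reader might also infer that the fault weakens the evaluable-set result.* It does not. Under Section 2.1.1 membership depends on at least 20 weeks of treatment and the timing of the EOT visit. Compliance is summarised in the safety analysis set and enters no ANCOVA. The exposure-adjusted adverse event rates use days of exposure. This objection stands in full.

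*The 186% figure is an extreme.* That is correct: it needs all six extras, and Table 1's footnote supports five. But a single extra dose already takes a fully dosed subject above 100%.

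**Conclusion.** The definition is wrong as written, and the fault is minor. Read literally, a fully dosed subject shows between 114% and 186% with one to six additional doses, or at most 171% if there can be only five. Missed regular doses are offset one for one by extras.

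This rests on three assumptions: seven regular doses, additional visits that are unscheduled as Appendix 8.3 and the footnote to Table 1 describe them, and no rule elsewhere that reclassifies them.

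The effect is confined to the descriptive by-arm compliance percentage. No efficacy estimate, analysis set or adverse event rate changes.

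There is no single correct replacement value. Additional doses are given as needed, so whether they are expected is a matter of definition: for two missed and two extra doses, 71% and 78% are both coherent answers, but 100% is not.

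**What to change.** In Section 3.3.1, state that additional COVID-19 dosing occasions count either in both numerator and denominator or in neither. Whichever is chosen, report compliance with the regular scheduled doses, with extras in neither term, as its own figure, because counting extras in both terms still dilutes missed regular doses. In Section 4.2.3, summarise the number of additional doses per subject by arm separately.

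Reconcile Section 1.2, the footnote to Table 1 and Appendix 8.3 on the number and last week of additional doses. This review takes no view on which is right.

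The cost is a sentence or two in Section 3.3.1, one summary line in Section 4.2.3 and a change to the counts in the compliance program. The definition needs no data beyond the dosing records that the plan already lists.
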